5.2 Per Protocol Set (PPS)

The PPS will include all subjects who meet the following criteria:

- Subjects in the FAS-I set,
- Completed the study without major deviations of the protocol.

These criteria will be used to capture relevant non-adherence to the protocol and are defined in 5.2.1. Final judgments on exclusion of subjects from the PPS are to be made at the ASCM, held prior to unblinding.

The PPS will be a secondary analysis set for efficacy. Selected demographic and baseline characteristics may also be summarized for the PPS.

5.2.1 Reasons for Exclusion From PPS

The following criteria listed in Table 3 may lead to subject's exclusion from PPS.

Table 3. Criteria for Assessing Major Protocol Violations which could potentially Impact Efficacy Assessments

Number	MPV Criteria
Treatment Violations	
1	Double Blind treatment duration of less than 53 days
2	No measurement of the primary efficacy endpoint available at or after Visit 2
3	Treatment compliance of less than 70% between randomization and last visit
4	Administration of excluded concomitant treatment as described in the Study Protocol.
Inclusion Criteria Violations	

5	Subject did not experience at least one incontinence episode based on the 3-day micturition diary at baseline.
6	Subject did not experience at least 3 episodes of urgency (grade 3 or 4) based on the 3-day micturition diary at baseline.
7	Subject did not experience an average of greater than or equal to 8 micturitions/day based on the 3-day micturition diary at baseline.
Exclusion Criteria Violations	
8	Subject was non-compliant during 2-week placebo run-in period, defined as taking less than 80% or greater than 120% of study medication
9	Subject did not complete all 3 days of the baseline 3-day micturition diary
10	Unblinding of Study Drug
11	Error in Study Drug Administration
Other Exclusions from PPS	
12	Subject did not complete at least 2 days of the EOT 3-day micturition diary

5.3 Safety Analysis Set (SAF)

The SAF will consist of all randomized subjects who received at least one dose of double-blind study medication. The SAF will be used for summarizing demographic and baseline OAB characteristics and safety data.

5.4 Randomized Analysis Set (RAS)

The Randomized Analysis Set (RAS) will consist of all randomized subjects. The RAS will be used to summarize disposition of subjects who were randomized to double-blind treatment.

6 ANALYSIS VARIABLES

6.1 Efficacy Endpoints

6.1.1 Primary Efficacy Endpoints

The co-primary efficacy endpoints are:

- Change from baseline to the end of treatment in mean number of micturitions/24 hour

based on a 3-day micturition diary.

- Change from baseline to end of treatment in mean number of incontinence episodes/24 hour based on a 3-day micturition diary.

6.1.2 Secondary Efficacy Endpoints

Secondary endpoints are:

- Change from baseline (Week 0) to the end of treatment (Week 12) in mean volume voided per micturition.
- Change from baseline to the end of treatment in symptom bother and total health related quality of life scores as assessed by Overactive Bladder-questionnaire (OAB-q).
- Change from baseline to the end of treatment in Patient Perception of Bladder Condition (PPBC).

6.1.3 Other Efficacy Variables

Other efficacy variables are the change from Baseline (Week 0) to End of Treatment (Week 12) in:

- Mean number of urgency episodes (grade 3 and/or 4)/24 hour
- Mean number of urgency incontinence episodes/24 hour
- Mean level of urgency
- Mean number of nocturia episodes/24 hour
- Barthel Index of Daily Living
- Vulnerable Elders Survey (VES-13)
- Patient Perception of Intensity of Urgency Scale (PPIUS)
- Subscale score from OAB-q scores
- Treatment Satisfaction – Visual Analog Scale (TS-VAS)
- University of Alabama, Birmingham - Life Space Assessment (UAB-LSA)
- Responder analysis as defined by $\geq 50\%$ reduction from baseline in mean number of incontinence episodes/24 hours from baseline
- Responder analysis defined by less than 8 micturitions per 24 hours post-baseline.
- Responder analysis defined as zero incontinence episodes at final visit
- Number of pads used

6.1.3.1 Patient Diary - Micturition and Incontinence

During the study, subjects will be requested to complete a ‘Subject diary’ which will be implemented on an electronic handheld device. This diary will collect data on micturition and

incontinence. The information from the diaries will be used to evaluate the efficacy of treatment. Therefore, subjects will receive full instructions and training on how to complete the diary at Screening (Visit 1) and will be counseled on the importance of completing the diaries prior to the next visit. The training diary will be reviewed with the subject by the Investigator or designee to ensure accuracy and completion. The diaries and questionnaires will be reviewed during each visit after Screening (Visit 1) by the Investigator or designee to ensure accuracy of completion.

Diaries will be completed 3 consecutive days prior to each visit: Baseline (Visit 3), Week 4 (Visit 4), Week 8 (Visit 5), and Week 12/End of Treatment (Visit 6).

A diary day starts at midnight and ends at midnight the following day. Time to bed with intention to sleep, time to awake with intention of staying awake, type of episode (urination/incontinence), time of episode, urgency severity, and sleep interruption will be recorded by the subject in the micturition diary.

At Visit 3, diary data, including the frequency of micturition (urination episodes), urgency episodes (grade 3 and 4) and incontinence episodes per 24 hours, will be reviewed to confirm inclusion criteria.

Micturitions will be counted as only urination episodes and not episodes of incontinence.

In addition to the micturition information, the electronic diary will also collect time of medication intake.

Definitions of efficacy variables based on the 3-day micturition diary are presented in Table 4.

Table 4. Micturition Diary Definitions and Calculations

Measurement	Definition	Calculation
Micturition	Any voluntary micturition (excluding incontinence only episodes).	A micturition episode is counted as micturition regardless of whether volume voided was recorded or not. A micturition recorded before midnight of the first day or after midnight on the 3rd day of the 3-day micturition diary period will not be counted. A micturition will also be counted if the subject assessed an episode as both micturition and incontinence.
Valid Diary Day	A diary day in which at least one voluntary micturition	A diary day is considered valid if at least one

	episode occurs. A diary day with episodes of incontinence only is not considered a valid diary day.	micturition was recorded on this calendar day. Days of visits to the clinic (determined by the date of questionnaire completion) will not be counted as valid diary days.
Number of Valid Diary Days	Number of valid diary days per each 3-day micturition diary period.	Count of the valid diary days during the 3-day micturition diary period. Days of visits to the clinic will not be counted as valid diary days.
Valid Diary	A valid diary is a diary with at least 2 valid diary days within the analysis visit window. If more than 3 valid diary days are recorded then the last 3 days will be used in the calculations.	Not applicable.
Mean Number of Micturitions per 24 hours	Average number of times a subject urinates (excluding incontinence only episodes and excluding duplicate records [same time and episode characteristics]) per day during the 3-day micturition diary period.	Number of micturitions recorded on valid diary days during the 3-day micturition diary period divided by the number of valid diary days during the 3-day micturition diary period.
Urinary Incontinence Episode or Incontinence Episode	The complaint of any involuntary leakage of urine.	An incontinence episode is counted if it was recorded in the diary on a valid diary day. An incontinence will also be counted if the subject assessed an episode as both micturition and incontinence.
Number of Incontinence Episodes	Number of times a subject records an incontinence episode during the 3-day micturition diary period.	Total number of incontinence episodes recorded during the 3-day micturition diary period.
Mean Number of Incontinence Episodes per 24 hours	Average number of times a subject records an incontinence episode per day during the 3-day micturition diary period.	Number of incontinence episodes recorded on valid diary days during the 3-day micturition diary period divided by the number of

		valid diary days during the 3-day micturition diary period.
Mean Volume Voided per Micturition	Mean volume voided (mL) per micturition during 3 days of the 3-day micturition diary period.	Sum of each volume voided for each record with volume voided > 0 on valid diary days divided by the total number of records with a volume voided > 0 on valid diary days during 3 days with volume measurements in the 3-day micturition diary period.
Severity of Urinary Urgency (based on PPIUS)	
Each micturition and/or incontinence episode is graded using the following 5 point scale based on PPIUS:
 
0 = No urgency, I felt no need to empty my bladder, but did so for other reasons.
 
1 = Mild urgency, I could postpone voiding as long as necessary, without fear of wetting myself
 
2 = Moderate urgency, I could postpone voiding for a short while, without fear of wetting myself
 
3 = Severe urgency, I could not postpone voiding, but had to rush to the toilet in order not to wet myself
 
4 = Urgency incontinence, I leaked before arriving to the toilet.
	Not applicable.
Urgency Urinary Incontinence Episode or Urgency Incontinence Episode	The involuntary leakage of urine accompanied by or immediately preceded by urgency.	One urgency incontinence episode is counted for each record of the diary in which the following occurs:

		
incontinence episode is recorded
 
AND
 
severity of urinary urgency recorded is 3 or 4
 
NOTE: Only urgency incontinence episodes recorded on a valid diary day will be counted.

Number of Urgency Incontinence Episodes	Number of times a subject records an urgency incontinence episode during the 3-day micturition diary period.	Number of urgency incontinence episodes recorded on valid diary days of the 3-day micturition diary period.
Mean Number of Urgency Incontinence Episodes per 24 hours	Average number of times a subject records an urgency incontinence episode per day during the 3-day micturition diary period.	Number of urgency incontinence episodes recorded on valid diary days during the 3-day micturition diary period divided by the number of valid diary days during the 3-day micturition diary period.
Urgency Episodes (severity of 3 or 4)	The complaint of a sudden, compelling desire to pass urine, which is difficult to defer.	
One urgency episode is counted for each record of the diary in which the following occurs:
 
micturition or incontinence episode is recorded
 
AND
 
severity of urinary urgency recorded is 3 or 4
 
NOTE: Only urgency episodes recorded on a valid diary day will be counted. If an episode was recorded as both a micturition and an incontinence episode with a urinary urgency of 3 or 4, it will be counted as one urgency episode.

Mean Number of Urgency Episodes (severity of 3 or 4) per 24 hours	Average number of times a subject records an urgency episode (severity of 3 or 4) with or without incontinence per day during the 3-day micturition diary period.	Sum of each record with an urgency episode (severity of 3 or 4) recorded on a valid diary day divided by the number of valid diary days during the 3-day micturition diary period.
Nocturia	Waking at night one or more times to void (i.e. any voiding associated with sleep disturbance between the date/time the subject goes to bed with the intention to sleep until the date/time the subject gets up in the morning with the intention to stay awake). A “night time” episode of incontinence only is not considered a nocturia episode.	A nocturia episode is counted for each micturition record which occurred between the date/time of going to bed with the intention to sleep (exclusive) and the date/time of getting up with the intention to stay awake (exclusive) on a valid diary day and which was accompanied by a sleep interruption. Nocturia will only be determined for subjects who are not night-shift workers.
Number of Nocturia Episodes	Number of nocturia episodes during the 3-day micturition diary period.	Sum of each nocturia episode recorded.
Mean number of nocturia episodes per 24 hours	Average number of times a subject records a nocturia episode per day during the 3-day micturition diary period.	Number of nocturia episodes recorded on valid diary days during the 3-day micturition diary period divided by the number of valid diary days during the 3-day micturition diary period.
Number of Pads Used	Number of times a subject records a new pad used during the 3-day micturition diary period.	Sum of each record with new pad checked. NOTE: Only records with new pad checked on a valid diary day will be counted.
Mean number of pads used per 24 hours	Average number of times a subject records a new pad used per day during the 3-day micturition diary period.	Number of new pads used during valid diary days during the 3-day micturition diary period divided by the number of valid diary days during the 3-day micturition diary period.

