███████████ ^f	X						
12-Lead ECG	X	X	X	X	X	X	
Ultrasound or Bladder Scan (PVR)	X						X
Medication History and OAB Medication History	X		X				
Clinical Assessment for Dose Increase				X	X		
Concomitant Medications Assessment	X	X	X	X	X	X	X
Adverse Event Assessment		X	X	X	X	X	X
Dispense Study Drug		X	X	X	X		
Drug Accountability			X	X	X	X	
Instruct Subject on 3-day Micturition Diary ^g		X	X	X	X	X	
Complete 3-day Micturition Diary including vital sign measurements and PPIUS ^{h,i}			X ^h	X ^h	X ^h	X ^h	
OAB-q			X	X	X	X	
Patient Perception of Bladder Condition Scores (PPBC)			X	X	X	X	
TS-VAS			X	X	X	X	
Montreal Cognitive Assessment Test (MoCA)			X				X
Univ Alabama Birmingham Life Space Assessment (UAB -LSA)			X	X	X	X	

Table continues on next page

	Screening	Placebo Run-In	Treatment Period				Follow-up Phone Call
Visit	1	2	3	4	5	6	7
Day	-28	-14	1	28	56	84	112
Week	-4	-2	0/Baseline	4	8	12/EOT	16
Visit Windows (Days) ^a	+/- 10	+/- 3	+/- 3	+/- 7	+/- 7	+/- 7	+/- 3
Barthel ADL Assessment			X			X	
Vulnerable Elders Survey 13 (VES-13)			X			X	
Review Subject Diary ^j			X	X	X	X	

- a. Visits 1 and 2 are negatively scheduled from the Baseline (Visit 3) date. A subject has a combined timeframe of up to 38 days to complete both Visits 1 and 2; however, Baseline (Visit 3) must occur at least 18 days but no more than 38 days after Visit 1 (Screening) and at least 11 days but no more than 17 days after Visit 2 (Placebo Run-In). After Visit 2 (Placebo Run-In), visit windows/study days will be calculated based on the Visit 3 (Baseline) visit date. Study procedures (e.g. bladder scan) for a particular visit do not need to be completed on the visit date if this is not feasible for the subject, as long as, study procedures are performed per protocol within the applicable visit window. Any procedure not done or performed outside the applicable visit window will be noted as a protocol deviation.
- b. Subjects must take at least 11 days, but no more than 17 days of placebo run-in medication.
- c. Randomization is to occur after confirming all eligibility criteria and after performing all other visit procedures at Visit 3.
- d. Height will only be assessed at the Screening Visit.
- e. Urine culture and sensitivity will be performed for positive leukocytes, or nitrites, or turbidity, or at the discretion of the PI. If a subject has a UTI, the subject can be rescreened after successful treatment of the UTI (confirmed by a laboratory result of negative urine culture).

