7.10.3.1 Analysis Visit Windows for Efficacy and Safety Variables

All the efficacy and safety assessments for a treatment period will be allocated based on the tables below.

Efficacy:

Analysis visit	Target day	Actual assessment day
Screening	Day -28	-38 to -18
Placebo Run-In	Day -14	-17 to 0
Baseline	Day 1	Day 1 ^a
Week 4	Day 30	15-42
Week 8	Day 60	43-70
Week 12/End of Treatment	Day 90	71-98
Follow Up Phone Call	Day 120	EOT+14

After Placebo Run-In, visit windows/study days will be calculated based on the Baseline (Visit 3) date.

Safety:

Analysis visit	Target day	Actual assessment day
Screening	Day -28	-38 to -18
Placebo Run-In	Day -14	-17 to 0
Baseline	Day 1	Day 1 ^a
Week 4	Day 30	2-45
Week 8	Day 60	46-75
Week 12/End of Treatment	Day 90	76-97
Follow Up Phone Call	Day 120	EOT+14

1. After Placebo Run-In, visit windows/study days will be calculated based on the Baseline (Visit 3) date.

For efficacy variables recorded in the 3-day micturition diary, the following rules will apply:

1. As micturition diary data are to be recorded from midnight 3 days prior to a visit to midnight 1 day prior to a visit, micturition diary records which have the same date as a visit date should be excluded from the analysis. Non-micturition questionnaire assessment dates will be compared to the eDiary dates and used to flag which diary records should be excluded.
2. Any diary days which are > 7 days after the last dose of double-blind treatment will not be included in the analysis.
3. Average values or number of episodes for count data will only be calculated if at least 2 valid diary days are available within the specified window. In the case that only 1 valid diary day is available, then no value will be calculated.
4. If there are more than 3 valid diary days available for a visit, the average will be based on the last 3 days prior to the scheduled visit.
5. Duplicate records (same time and episode characteristics) per day during the 3-day micturition diary period will be excluded.

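### The SAP flags the clinic-visit day by questionnaire date instead of visit date, so a partial visit day can enter the diary means or a full diary day can be lost

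*SAP*

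**What the plan says.** **Aim.** SAP 7.10.3.1, diary rule 1, states that "micturition diary records which have the same date as a visit date should be excluded from the analysis".

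**Tool.** The same rule then identifies those records indirectly: "Non-micturition questionnaire assessment dates will be compared to the eDiary dates and used to flag which diary records should be excluded". SAP 6.1.3.1, Table 4 (Valid Diary Day) does likewise: "Days of visits to the clinic (determined by the date of questionnaire completion) will not be counted as valid diary days".

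**Where the dates can part.** Footnote a to the protocol's Table 1 reads: "Study procedures (e.g. bladder scan) for a particular visit do not need to be completed on the visit date if this is not feasible", with the limit "as long as, study procedures are performed per protocol within the applicable visit window". That window is 3 days either side at Visit 3 and 7 days either side at Visits 4 to 6. The OAB-q, PPBC, TS-VAS and UAB-LSA are rows of that schedule and are not exempted. The SAP's own schedule footnote a does not carry this sentence.

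**What happens to a day that is not flagged.** Under Table 4, one recorded micturition makes a day valid, and the 24-hour means divide by the number of whole valid days. On surplus days, Table 4 says: "If more than 3 valid diary days are recorded then the last 3 days will be used in the calculations". Diary rule 4 in 7.10.3.1 instead takes the three latest days ahead of the scheduled visit. SAP 7.1 derives visit values from the three diary days before each visit. Table 4 (Micturition) stops counting at the midnight that closes the third diary day. Rule 3 requires two valid days, failing which no value is calculated.

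**The concern.** A diary day runs from midnight to midnight, so the day of a clinic visit is only partly recorded, and the SAP is right to want it out. The date of a different assessment stands in for the visit date, and the proxy can fail in two directions.

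- The questionnaire is missing or dated after the visit. Nothing is flagged, and a partly recorded visit day can count as a full 24 hours.
- The questionnaire is dated on one of the diary days. That day is removed although the diary for it may be complete, and any records on the true visit day are not flagged.

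No rule says what to do when several questionnaires carry different dates. The derived days feed both co-primary endpoints, mean volume voided and the other diary variables. At baseline, a lost or partial day could also bear on the FAS-I requirement for an incontinence episode and on the diary-based PPS criteria in SAP Table 3.

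**Working it through.** **1. Plan's own figure.** SAP section 4 gives 340 per arm, a difference of 0.796 micturitions per 24 h, SD 2.7, two-sided alpha 0.05 and 97% power. Check: SE = 2.7 × √(2/340) = 0.207; 0.796/0.207 = 3.84; Φ(3.84 − 1.96) = 97.0%. It reproduces, and nothing in this point disputes it.

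**2. Which cases fail.** Let V be the visit day and D−3, D−2, D−1 the diary days. Take the questionnaire date as the only flag, as both passages direct.

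| Questionnaire | Valid days before flagging | Days used | Result |
|---|---|---|---|
| on V | D−3 to D−1, V | D−3 to D−1 | as intended |
| missing or after V | D−3 to D−1, V | Table 4: D−2, D−1, V; rule 4: D−3 to D−1 | the two rules disagree; rule 4 is correct |
| missing or after V | two diary days, V | all three, with V | partial day counted; rule 4 not triggered |
| on D−1 | D−3 to D−1, V | D−3, D−2, V | full day lost, partial day counted; exactly three days, so rule 4 not triggered |
| on D−1 | D−3 to D−1 | D−3, D−2 | one full day lost, no partial-day error |
| on D−1 | D−1 and one other | one day | no value for that visit |

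The midnight cut-off in Table 4 would remove V in these cases if the 3-day period is anchored to the visit date. The SAP does not say how it is anchored.

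**3. Size in one affected subject.** The documents give no figure for a part-day, so the inputs are assumptions: 8 to 12 micturitions per full day (8 is the entry minimum) and a visit day holding a share f of 25% to 60% of a full day's episodes.

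- Three days, one partial: shift = −(1 − f) × rate / 3. Smallest: −0.40 × 8 / 3 = −1.07. Largest: −0.75 × 12 / 3 = −3.0.
- Two days, one partial: shift = −(1 − f) × rate / 2, from −1.6 to −4.5.
- Incontinence, assuming 1 to 3 episodes per day, three days: from −0.40 × 1 / 3 = −0.13 to −0.75 × 3 / 3 = −0.75.

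**4. Size for the trial, same affected share q in both arms.** For a shift d at end of treatment, SD = √(2.7² + q(1 − q)d²), holding the difference at 0.796.

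- q = 2%, d = 1.33: SD 2.71, power 97.0%.
- q = 10%, d = 2.0: SD 2.77, power 96.4%.
- q = 20%, d = 2.5: SD = √(7.29 + 0.16 × 6.25) = 2.88, power 95.0%.
- Extreme corner, q = 20%, d = 3.0: SD = √(7.29 + 0.16 × 9) = 2.95; SE 0.227; Φ(3.51 − 1.96) = 94.0%.

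**5. Unequal shares.** Bias in the treatment difference = (difference in share) × d. For 2 to 10 percentage points and d of 1.33 to 2.5 this is 0.03 to 0.25, or 3% to 31% of 0.796. The documents give no reason to expect such a difference.

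**The case against.** The strongest reply is that rule 1 already states the right principle without condition, and that the questionnaire comparison is only the means of applying it. Other provisions point the same way: the midnight cut-off in Table 4, the derivation in 7.1 from the days before each visit, and rule 4. The route is also narrow. Footnote a applies only where same-day completion is not feasible, and its one example is a bladder scan, so its reach to questionnaires is inferred from the schedule rows. Subjects are told to record the three days leading up to the visit, so visit-day records need recording beyond the instructions. At Visit 3 a late questionnaire is ruled out: "Randomization is to occur after confirming all eligibility criteria and after performing all other visit procedures at Visit 3".

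Most of this stands, and it limits the point. A reader might infer that an unflagged visit day routinely pushes out the first full diary day. The documents do not support that, because rule 4 addresses the four-day case and only Table 4's looser wording leaves it open. A reader might also expect frequent loss of subjects. But the PPS criteria may, not must, lead to exclusion, the judgement is made before unblinding, and under SAP 7.1.1 a subject who withdraws before week 12 has an earlier post-baseline value carried forward (7.1 does the same wherever no Week 12 diary data are available).

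What does not stand is that stating the aim cures the method. A programmer following Table 4 and rule 1 literally would use questionnaire dates, with no instruction for a missing or discrepant one.

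**Conclusion.** The point holds as a gap between a rule's aim and its operation. The questionnaire date can miss a partial visit day or remove a full diary day. The exposure lies mainly in diaries with three or fewer valid days that include an unflagged visit day, and in the Table 4 wording on surplus days.

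On the stated assumptions, an affected 3-day mean falls by about 1 to 3 micturitions per 24 h. It is tempting to set that beside the planned difference of 0.796 and infer a large treatment bias. That comparison is not valid: one is an error in a single subject, the other a difference between arm means. The fitting yardstick is the subject-level SD of 2.7. With 1:1 blinded allocation the affected share is probably similar between arms, so the shift largely cancels. What remains is added noise, with power going from 97% to no lower than about 95% for 2% to 20% affected and a shift of 1.33 to 2.5, plus an occasional lost valid day. The affected share is unknown from the documents. The planned sample size need not change.

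**What to change.** - In SAP Table 4 and diary rule 1, exclude diary records dated on the recorded visit date. Protocol 8.1.2 already lists visit dates among the source records.
- Use questionnaire dates only as a cross-check. Where one differs from the visit date, exclude that day as well only if the subject was in the clinic on it. Resolve each discrepancy blind, before database lock. A flat rule never to exclude on a questionnaire date would go too far, because a visit split over two days has two clinic days.
- Align Table 4 and SAP 7.1.1 with rule 4, so that the last three valid days are those strictly before the recorded visit date.

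The cost is a few sentences in the SAP, a small programming change and a blinded reconciliation of discrepant dates. No new data are needed.
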